6.3. Descriptive statistics

We will describe participant flow and reasons for non-participation by group allocation in a flowchart.

For HCW included in the analysis, we will describe background factors. Distribution of background factors will be presented by group allocation overall and by gender (male/female) and occupational group (doctors/ nurses/other).

In the exploratory data analysis, all variables will be analysed to know their distribution. Background factors will be summarised by counts (percentages), means (standard deviation) or medians (interquartile range) as appropriate. Information on the proportion with missing information will be provided.

For qualitative variables, absolute and relative frequencies will be used to understand the distribution, and from there, to define if there is a need to group some categories in order to make a statistical comparison possible.

In the case of quantitative variables, the analysis of their distribution will be done by observing measures of central tendency, measures of position, and measures of variation. In this step, if the quantitative variable is continuous, we will study its distribution that will determined the type of statistical tests to apply in the bivariate step. If the variable has normal distribution the appropriate measure for representation is the mean with its respective standard deviation and the line of parametric tests, otherwise the appropriate measure is the median accompanied by the information of the interquartile range (first and third quartile) and the tests to be applied are the non-parametric tests. To test the normality of the data we will use the Kolmogorov-Smirnov tests.

6.4. Inferential statistics

The comparison between the intervention versus placebo groups will be done using the chi-square test (χ^2 test or Fisher's Exact test (categorical variable) or Student's t-test or Mann-Whitney test (quantitative variable) according to the distribution of variables.

Fisher's test is useful for categorical data, which result from classifying objects in two different ways and when considering the sample number low; it is used to examine the significance of the association (contingency) between the two types of classification. It is used because the approximation is inadequate when the sample size is small, or if the data are very unevenly distributed among the cells of the table, resulting in the cell count predicted by the null hypothesis (the "expected values") being low. Although considered conservative, we can - for its use - use the usual rule for deciding whether the chi-square approximation test is good enough, where the chi-square test is not appropriate when the expected values in the cells of the contingency table are below 5, or below 10 when there is only one degree of freedom. In fact, for small, sparse, or unbalanced data, the exact and asymptotic p-value can be very different and can lead to opposite conclusions about the hypothesis of interest. Fisher's exact test keeps the row and column totals fixed, and can therefore be used regardless of the sample characteristics. It becomes difficult to calculate with large samples or well-balanced tables; under these conditions, the χ^2 test is appropriate.

When you have a small sample and the numerical variable is not known to have a normal distribution (or cannot be verified satisfactorily), or when there is no homogeneity of variances, Student's t-test is not appropriate. In this situation, the nonparametric Mann-Whitney test (Wilcoxon rank-sum test, U-test) can be used. Unlike the t-test, which tests for equality of means, the Mann-Whitney test tests for equality of medians. The U values calculated by the test assess the degree of intermingling of the data of the two groups after sorting. The greater separation of the data together indicates that the samples are distinct, rejecting the hypothesis of equality of the medians. Total days of absenteeism will be analyzed using a Bayesian negative binomial regression with a fixed effect for BCG, hospital, professional category, age, enrolment week and number of average workdays per week. The excess absence of the event of interest can lead to data overdispersion (a phenomenon that occurs when the variance of the response variable is greater than the value of the mean). To check the overdispersion of the data we will use the deviance, which is also a statistic used to check the goodness of fit of the model.

The Kaplan-Meier method consists of dividing the follow-up time into intervals, whose limits correspond to the follow-up time when events occurred. The measure of association used in survival analysis to

compare groups is the Hazard Ratio (HR), with similar meaning to Relative Risk; HR is the probability that some participant who did not have the outcome event by a certain time, will have it at that time. HR therefore compares the instantaneous incidence with which events occur in the different groups (BCG and Placebo).

For the univariate analysis to check the difference between the BCG versus Placebo groups we will use the Logrank test of significance by means of its p-value or confidence interval. For the univariate analysis to check the difference between the BCG versus Placebo groups we will use the Logrank test of significance by means of its p-value or confidence interval. In the multivariate analysis for the comparison of the two analyzed groups, we will use the Cox Proportional Hazard Regression, or Cox Regression. This allows us to obtain results adjusted for possible confounding variables. Cumulative incidence data will be analysed in Cox proportional hazards models. The Cox Model, which is semi-parametric, assumes that failure rates are proportional, that is, the risk of failure of the variables is constant over time. Survival analysis will allow us to correctly assess the rate at which events (outcomes) are occurring in the different groups in our study.

7. Demographics and other baseline characteristics

Baseline characteristics

Table 2 – Baseline characteristics of the participants

Variable	Type	BCG vaccine	Placebo	Statistical (P-value)
Age (years)	Quantitative	$\bar{X} \pm SD$ or Md (IQR)	$\bar{X} \pm SD$ or Md (IQR)	Student's t-test or Mann-Whitney test
Gender				
Female	Categorical	% (n/N)	% (n/N)	χ^2 test or Fisher's exact test (P-value)
Male		% (n/N)	% (n/N)	
Number adults (> 18 years) living in the household	Quantitative	$\bar{X} \pm SD$ or Md (IQR)	$\bar{X} \pm SD$ or Md (IQR)	Student's t-test or Mann-Whitney test
Adult living at home and also healthcare worker	Quantitative	$\bar{X} \pm SD$ or Md (IQR)	$\bar{X} \pm SD$ or Md (IQR)	Student's t-test or Mann-Whitney test
Number children (<18 years) living in the household	Quantitative	$\bar{X} \pm SD$ or Md (IQR)	$\bar{X} \pm SD$ or Md (IQR)	Student's t-test or Mann-Whitney test
Age of the youngest child living in the household (years)	Quantitative	$\bar{X} \pm SD$ or Md (IQR)	$\bar{X} \pm SD$ or Md (IQR)	Student's t-test or Mann-Whitney test
Animals living in the household				
Dogs	Categorical	% (n/N)	% (n/N)	χ^2 test or Fisher's exact test (P-value)
Cats		% (n/N)	% (n/N)	
Pigs		% (n/N)	% (n/N)	

Variable	Type	BCG vaccine	Placebo	Statistical (P-value)	
Birds		% (n/N)	% (n/N)		
Sheep		% (n/N)	% (n/N)		
Other		% (n/N)	% (n/N)		
Person living in the household diagnosed with COVID-19					
No	Categorical	% (n/N)	% (n/N)	χ^2 test or Fisher's exact test (P-value)	
Yes		% (n/N)	% (n/N)		
Occupation					
Doctor	Categorical	% (n/N)	% (n/N)	χ^2 test or Fisher's exact test (P-value)	
Nurse		% (n/N)	% (n/N)		
Other		% (n/N)	% (n/N)		
Unit / Department with the highest frequency at work					
Urgency center	Categorical	% (n/N)	% (n/N)	χ^2 test or Fisher's exact test (P-value)	
Medicine		% (n/N)	% (n/N)		
Surgery		% (n/N)	% (n/N)		
Consultation / outpatient		% (n/N)	% (n/N)		
Maternity		% (n/N)	% (n/N)		
Pediatric		% (n/N)	% (n/N)		
Other		% (n/N)	% (n/N)		
Hours worked per week at the hospital or health center (on a typical work week)					
	Quantitative	$\bar{X} \pm SD$ or Md (IQR)	$\bar{X} \pm SD$ or Md (IQR)	Student's t-test or Mann-Whitney test	
Work in another place					
No	Categorical	% (n/N)	% (n/N)	χ^2 test or Fisher's exact test (P-value)	
Yes		% (n/N)	% (n/N)		
Yes, another public hospital/ health institution/ clinic /private practice		% (n/N)	% (n/N)		
Yes, another private hospital/ health institution/ clinic / consulting rooms		% (n/N)	% (n/N)		
Yes, another place that it is not a hospital/ health institution/ clinic/ private practice		% (n/N)	% (n/N)		
Provide direct care patients infected with COVID-19 or patients that are suspected to be infected					
No	Categorical	% (n/N)	% (n/N)	χ^2 test or Fisher's exact test (P-value)	
Yes		% (n/N)	% (n/N)		
Contact with areas where COVID-19 patients are treated					
No	Categorical	% (n/N)	% (n/N)	χ^2 test or Fisher's exact test (P-value)	
Yes		% (n/N)	% (n/N)		
Access to personal protection equipment available at your					
	Categorical				

Variable	Type	BCG vaccine	Placebo	Statistical (P-value)
workplace to prevent COVID-19 and other infectious diseases				χ^2 test or Fisher's exact test (P-value)
No		% (n/N)	% (n/N)	
Yes		% (n/N)	% (n/N)	
Use of mask by the patient during the interview				χ^2 test or Fisher's exact test (P-value)
Correct use	Categorical	% (n/N)	% (n/N)	
Incorrect use		% (n/N)	% (n/N)	
Does not wear a mask		% (n/N)	% (n/N)	
Absent from work for the past 2 weeks due to illness				χ^2 test or Fisher's exact test (P-value)
No	Categorical	% (n/N)	% (n/N)	
Yes		% (n/N)	% (n/N)	
Days absent from work for the past 2 weeks	Quantitative	$\bar{X} \pm SD$ or Md (IQR)	$\bar{X} \pm SD$ or Md (IQR)	Student's t-test or Mann-Whitney test
Hospitalization for the past 2 weeks due to illness				χ^2 test or Fisher's exact test (P-value)
No	Categorical	% (n/N)	% (n/N)	
Yes		% (n/N)	% (n/N)	
Days hospitalization for the past 2 weeks	Quantitative	$\bar{X} \pm SD$ or Md (IQR)	$\bar{X} \pm SD$ or Md (IQR)	Student's t-test or Mann-Whitney test
Symptoms in the past 2 weeks	Categorical			χ^2 test or Fisher's exact test (P-value)
Fever (> 38 C)		% (n/N)	% (n/N)	
Cough		% (n/N)	% (n/N)	
Respiratory problem		% (n/N)	% (n/N)	
Fatigue		% (n/N)	% (n/N)	
Headache		% (n/N)	% (n/N)	
Muscle pain		% (n/N)	% (n/N)	
Sore throat		% (n/N)	% (n/N)	
Diarrhea		% (n/N)	% (n/N)	
Loss of smell / taste		% (n/N)	% (n/N)	
Other		% (n/N)	% (n/N)	
Body structure				χ^2 test or Fisher's exact test (P-value)
1		% (n/N)	% (n/N)	
2		% (n/N)	% (n/N)	
3		% (n/N)	% (n/N)	
4	Categorical	% (n/N)	% (n/N)	
5		% (n/N)	% (n/N)	
6		% (n/N)	% (n/N)	
7		% (n/N)	% (n/N)	
8		% (n/N)	% (n/N)	
9		% (n/N)	% (n/N)	
Chronic disease				χ^2 test or Fisher's exact test (P-value)
No	Categorical	% (n/N)	% (n/N)	
Yes		% (n/N)	% (n/N)	
Type of chronic disease				
Diabetes		% (n/N)	% (n/N)	
Chronic obstructive pulmonary disease	Categorical	% (n/N)	% (n/N)	
Other respiratory disease		% (n/N)	% (n/N)	
Hypertension		% (n/N)	% (n/N)	

Variable	Type	BCG vaccine	Placebo	Statistical (P-value)
Other cardiovascular diseases		% (n/N)	% (n/N)	χ^2 test or Fisher's exact test (P-value)
Autoimmune disease		% (n/N)	% (n/N)	
Obesity		% (n/N)	% (n/N)	
Overweight		% (n/N)	% (n/N)	
Other		% (n/N)	% (n/N)	
Health scale				
1		% (n/N)	% (n/N)	χ^2 test or Fisher's exact test (P-value)
2		% (n/N)	% (n/N)	
3		% (n/N)	% (n/N)	
4	Categorical	% (n/N)	% (n/N)	
5		% (n/N)	% (n/N)	
6		% (n/N)	% (n/N)	
7		% (n/N)	% (n/N)	
8		% (n/N)	% (n/N)	
9		% (n/N)	% (n/N)	
10		% (n/N)	% (n/N)	
Use of medication				
No	Categorical	% (n/N)	% (n/N)	χ^2 test or Fisher's exact test (P-value)
Yes		% (n/N)	% (n/N)	
Do not know		% (n/N)	% (n/N)	
COVID-19 vaccine				
No	Categorical	% (n/N)	% (n/N)	χ^2 test or Fisher's exact test (P-value)
Yes		% (n/N)	% (n/N)	
COVID-19 vaccine type				
Astra Zeneca	Categorical	% (n/N)	% (n/N)	χ^2 test or Fisher's exact test (P-value)
Pfizer		% (n/N)	% (n/N)	
Moderna		% (n/N)	% (n/N)	
Sinopharm		% (n/N)	% (n/N)	
Other		% (n/N)	% (n/N)	
COVID-19 Vaccine dose				
First dose	Categorical	% (n/N)	% (n/N)	χ^2 test or Fisher's exact test (P-value)
Second dose		% (n/N)	% (n/N)	
BCG vaccine				
No	Categorical	% (n/N)	% (n/N)	χ^2 test or Fisher's exact test (P-value)
Yes		% (n/N)	% (n/N)	
Do not know		% (n/N)	% (n/N)	
BCG vaccination number				
One time	Categorical	% (n/N)	% (n/N)	χ^2 test or Fisher's exact test (P-value)
Two time		% (n/N)	% (n/N)	
Three or more time		% (n/N)	% (n/N)	
BCG scar				
No	Categorical	% (n/N)	% (n/N)	χ^2 test or Fisher's exact test (P-value)
Yes		% (n/N)	% (n/N)	
Previous vaccination scar				
No scar	Categorical	% (n/N)	% (n/N)	χ^2 test or Fisher's exact test (P-value)
BCG scar		% (n/N)	% (n/N)	
Smallpox scar		% (n/N)	% (n/N)	
Has not been examined		% (n/N)	% (n/N)	
BCG scar local				
Right arm	Categorical	% (n/N)	% (n/N)	

Variable	Type	BCG vaccine	Placebo	Statistical (P-value)
Left arm		% (n/N)	% (n/N)	χ^2 test or Fisher's exact test (P-value)
Both arms		% (n/N)	% (n/N)	
Smallpox scar local				χ^2 test or Fisher's exact test (P-value)
Right arm	Categorical	% (n/N)	% (n/N)	
Left arm		% (n/N)	% (n/N)	
Both arms		% (n/N)	% (n/N)	
BCG scar number				
1	Categorical	% (n/N)	% (n/N)	χ^2 test or Fisher's exact test (P-value)
2		% (n/N)	% (n/N)	
3 or more		% (n/N)	% (n/N)	
Smallpox scar number				χ^2 test or Fisher's exact test (P-value)
1	Categorical	% (n/N)	% (n/N)	
2		% (n/N)	% (n/N)	
3 or more		% (n/N)	% (n/N)	

Characteristics of the participants in the follow-up

Table 3 - Characteristics of the participants in the follow-up

Characteristics	Type	BCG vaccine	Placebo	Statistical (P-value)
Vaccine in the last 2 years				χ^2 test or Fisher's exact test (P-value)
No	Categorical	% (n/N)	% (n/N)	
Yes		% (n/N)	% (n/N)	
Received any vaccines in the last 2 years				χ^2 test or Fisher's exact test (P-value)
Oral Polio Vaccine	Categorical	% (n/N)	% (n/N)	
Yellow Fever Vaccine		% (n/N)	% (n/N)	
Measles Vaccine		% (n/N)	% (n/N)	
Rota virus vaccine		% (n/N)	% (n/N)	
Smallpox vaccine		% (n/N)	% (n/N)	
Oral Typhoid vaccine		% (n/N)	% (n/N)	
Varicella vaccine		% (n/N)	% (n/N)	
BCG vaccine		% (n/N)	% (n/N)	
Other vaccine		% (n/N)	% (n/N)	
Vaccine in the last two weeks				
No	Categorical	% (n/N)	% (n/N)	
Yes		% (n/N)	% (n/N)	
Vaccine type received in the last two weeks				χ^2 test or Fisher's exact test (P-value)
Oral Polio Vaccine	Categorical	% (n/N)	% (n/N)	
Yellow Fever Vaccine		% (n/N)	% (n/N)	
Measles Vaccine		% (n/N)	% (n/N)	
Rota virus vaccine		% (n/N)	% (n/N)	
Smallpox vaccine		% (n/N)	% (n/N)	
Oral Typhoid vaccine		% (n/N)	% (n/N)	
Varicella vaccine		% (n/N)	% (n/N)	
BCG vaccine		% (n/N)	% (n/N)	
Other vaccine		% (n/N)	% (n/N)	
Symptoms in the past 2 weeks			% (n/N)	% (n/N)
Fever (> 38 C)		% (n/N)	% (n/N)	

Cough		% (n/N)	% (n/N)	χ^2 test or Fisher's exact test (P-value)
Respiratory problem		% (n/N)	% (n/N)	
Fatigue		% (n/N)	% (n/N)	
Headache		% (n/N)	% (n/N)	
Muscle pain		% (n/N)	% (n/N)	
Sore throat	Categorical	% (n/N)	% (n/N)	
Diarrhea		% (n/N)	% (n/N)	
Loss of smell / taste		% (n/N)	% (n/N)	
Other		% (n/N)	% (n/N)	
Health problem in the past 2 weeks				χ^2 test or Fisher's exact test (P-value)
No		% (n/N)	% (n/N)	
Yes	Categorical	% (n/N)	% (n/N)	
Absent from work for the past 2 weeks due to illness				χ^2 test or Fisher's exact test (P-value)
No	Categorical	% (n/N)	% (n/N)	
Yes		% (n/N)	% (n/N)	
Days absent from work for the past 2 weeks	Quantitative	$\bar{X} \pm SD$ or Md (IQR)	$\bar{X} \pm SD$ or Md (IQR)	Student's t-test or Mann-Whitney test
Absent from work in the last 2 weeks due to a quarantine				χ^2 test or Fisher's exact test (P-value)
No	Categorical	% (n/N)	% (n/N)	
Yes		% (n/N)	% (n/N)	
Days absent from work in the last 2 weeks due to a quarantine	Quantitative	$\bar{X} \pm SD$ or Md (IQR)	$\bar{X} \pm SD$ or Md (IQR)	Student's t-test or Mann-Whitney test
Absent from work in the last 2 weeks due to illness				χ^2 test or Fisher's exact test (P-value)
No	Categorical	% (n/N)	% (n/N)	
Yes		% (n/N)	% (n/N)	
Days absent from work in the last 2 weeks due to illness	Quantitative	$\bar{X} \pm SD$ or Md (IQR)	$\bar{X} \pm SD$ or Md (IQR)	Student's t-test or Mann-Whitney test
Absent from work in the last 2 weeks due to COVID-19				χ^2 test or Fisher's exact test (P-value)
No	Categorical	% (n/N)	% (n/N)	
Yes		% (n/N)	% (n/N)	
Days absent from work in the last 2 weeks due to COVID-19	Quantitative	$\bar{X} \pm SD$ or Md (IQR)	$\bar{X} \pm SD$ or Md (IQR)	Student's t-test or Mann-Whitney test
Hospitalisation in the last 2 weeks due to illness				χ^2 test or Fisher's exact test (P-value)
No		% (n/N)	% (n/N)	
Yes	Categorical	% (n/N)	% (n/N)	
Nights hospitalisation in the last 2 weeks due to illness	Quantitative	$\bar{X} \pm SD$ or Md (IQR)	$\bar{X} \pm SD$ or Md (IQR)	Student's t-test or Mann-Whitney test
Hospitalisation due to COVID-19				χ^2 test or Fisher's exact test (P-value)
No	Categorical	% (n/N)	% (n/N)	
Yes		% (n/N)	% (n/N)	
Nights hospitalisation due to COVID-19	Quantitative	$\bar{X} \pm SD$ or Md (IQR)	$\bar{X} \pm SD$ or Md (IQR)	Student's t-test or Mann-Whitney test
Hospitalisation due other causes				χ^2 test or Fisher's exact test (P-value)
No	Categorical	% (n/N)	% (n/N)	
Yes		% (n/N)	% (n/N)	

Person living in the household diagnosed with COVID-19 in the last 2 weeks				
No		% (n/N)	% (n/N)	χ^2 test or Fisher's exact test (P-value)
Yes	Categorical	% (n/N)	% (n/N)	
Suspected but not confirmed				
No		% (n/N)	% (n/N)	χ^2 test or Fisher's exact test (P-value)
Yes	Categorical	% (n/N)	% (n/N)	
COVID test in the last 2 weeks				
No		% (n/N)	% (n/N)	χ^2 test or Fisher's exact test (P-value)
Yes	Categorical	% (n/N)	% (n/N)	
COVID test type				
RT-PCR (swab in the throat or nose)		% (n/N)	% (n/N)	χ^2 test or Fisher's exact test (P-value)
Rapid test for the antibodies detection in the blood (finger prick)		% (n/N)	% (n/N)	
	Categorical			
RT-PCR result				
Positive		% (n/N)	% (n/N)	χ^2 test or Fisher's exact test (P-value)
Negative		% (n/N)	% (n/N)	
Missing		% (n/N)	% (n/N)	
Rapid test result				
Positive		% (n/N)	% (n/N)	χ^2 test or Fisher's exact test (P-value)
Negative		% (n/N)	% (n/N)	
Missing		% (n/N)	% (n/N)	

8. Analysis of endpoints

Table 4 – Analysis of endpoints from Bayesian analysis

Endpoint Variable	BCG	Placebo	Risk Ratio (95%CI) p-value
Absenteeism	$\bar{X} \pm SD$ or Md (IQR)	$\bar{X} \pm SD$ or Md (IQR)	RR (95%CI) p-Value
Absenteeism for COVID-19	$\bar{X} \pm SD$ or Md (IQR)	$\bar{X} \pm SD$ or Md (IQR)	RR (95%CI) p-Value
Absenteeism besides COVID-19	$\bar{X} \pm SD$ or Md (IQR)	$\bar{X} \pm SD$ or Md (IQR)	RR (95%CI) p-Value
Absenteeism for infections	$\bar{X} \pm SD$ or Md (IQR)	$\bar{X} \pm SD$ or Md (IQR)	RR (95%CI) p-Value
Absenteeism for respiratory infections	$\bar{X} \pm SD$ or Md (IQR)	$\bar{X} \pm SD$ or Md (IQR)	RR (95%CI) p-Value

Table 5 – Analysis of endpoints from Cox regression and Poisson regression

Endpoint Variable	BCG	Placebo	Hazard Ratio (95%CI) p-value
Cumulative incidence of infectious disease episodes	rate (events / risk time)	rate (events / risk time)	HR (95%CI) p-Value
Cumulative incidence of respiratory infectious disease episodes	rate (events / risk time)	rate (events / risk time)	HR (95%CI) p-Value
Cumulative incidence of hospital admissions	rate (events / risk time)	rate (events / risk time)	HR (95%CI) p-Value
Cumulative incidence of infectious disease hospital admissions	rate (events / risk time)	rate (events / risk time)	HR (95%CI) p-Value
Cumulative incidence of respiratory infectious hospital admissions	rate (events / risk time)	rate (events / risk time)	HR (95%CI) p-Value
Cumulative incidence of hospital admissions due to documented COVID-19	rate (events / risk time)	rate (events / risk time)	HR (95%CI) p-Value
Cumulative incidence all-cause and infectious intensive care admission	rate (events / risk time)	rate (events / risk time)	HR (95%CI) p-Value
Cumulative incidence of intensive care admission due to documented COVID-19 infection	rate (events / risk time)	rate (events / risk time)	HR (95%CI) p-Value
COVID-19 infection*	% (n/N)	% (n/N)	RR (95%CI)
Death*	% (n/N)	% (n/N)	RR (95%CI)

*Analysed in Poisson regression with robust variance estimation, including stratification variables, i.e. country, profession and sex, providing Risk Ratios (RR).

9. Analysis of exploratory endpoints

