Data will be reported quantitatively. All analyses will be performed from the intention-to-treat principle. Missing data on background variables will be dealt with by multiple imputation. Final data analysis will begin when the last participant in the multicentric RCT has completed the follow-up period. The primary endpoint, work absenteeism due to illness, will be reported as the total number of sick days with standard deviation. Total days of absenteeism will be analysed using a Bayesian negative binomial regression with a fixed effect for BCG, hospital, professional category, age, enrolment week and number of average workdays per week. The brm function from the R package "brms" will be used for fitting the negative binomial model. The effect will be reported as a relative risk with 95% confidence interval (CI). Please refer to section interim analysis for type-1 error control and power.

Similar regression models will be used for secondary endpoints. Cumulative incidence outcomes will primarily be analysed using Cox Proportional Hazard Regression.

Continuous baseline characteristics will be reported as means with the standard deviation or medians with the inter-quartile range, as appropriate. Categorical baseline characteristics will be reported as count and percentage. No statistical testing for baseline characteristics will be reported.

Please refer to the Data Analysis Plan for more details.

Interim analysis

Every month, an interim analysis will be conducted for each study site and of the combined dataset. Interim analyses will start after the 200th participant has been recruited across the two sites. The primary endpoint will be analysed as described above. The Bayesian model yields a posterior distribution of the relative risk (RR). The posterior probability of the superiority hypothesis ($RR < 1$) will be calculated. If during any of the interim analyses, the posterior probability of superiority is > 0.995 , a conclusion is reached, and the trial will be stopped.

Monthly, the following secondary endpoints will be reported from the sites: hospital admissions, and deaths.

IMPLEMENTATION

Inception

The study will begin with an inception meeting to be held in Cape Verde or virtually, depending on travel and quarantine recommendations at the time. Besides administrative issues, the meeting will address:

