Known allergy to (components of) BCG or serious adverse events to prior BCG administration; known previous, active or latent infection with *Mycobacterium tuberculosis* or other mycobacterial species, fever (>38 C) within past 24 hours; previous confirmed COVID-19 (positive test by PCR or antibody) until inception of COVID-19 vaccination of HCW; suspicion of active viral or bacterial infection, severely immunocompromised subjects, self-reported HIV infection (Guinea: HIV-rapid test), self-reported pregnancy; active solid or non-solid malignancy or lymphoma within the last two years; any other contraindications for live-attenuated vaccine administration, not having a telephone.

Randomization

All participants who give consent for participation and who fulfil the inclusion criteria will be randomly assigned to either placebo or BCG group with a 1:1 (treatment:placebo) allocation in varying block sizes of 4 or 6 per block within strata defined by gender (male/female) and occupational group (doctors/nurses/other).

Blinding

The BCG vaccine was administered by study physicians/nurses, who are not blinded but also not involved in the data collection. Participants and follow-up assistants will be blinded to the treatment allocation. In case of serious adverse events, the participant can be unblinded after consultation with the investigator or the vaccinating physician/nurse. When the study has ended, all participants will receive information about the intervention that they received.

Intervention

The intervention consists of the administration of an intradermal injection of a standard 0.1 ml adult dose of attenuated *Mycobacterium bovis* BCG (Bacillus Calmette-Guerin), Danish strain 1331, $2-8 \times 10^5$ CFU or the placebo comparator: intradermal standard 0.1 ml saline solution (NaCl 0.9%). Both BCG and saline solution will be injected in the skin over the upper deltoid muscle.

Outcomes

Primary outcome measure: Total numbers of days of unplanned absenteeism from work due to illness.

Secondary outcome measures: Days of unplanned absenteeism because of documented COVID-19 and cumulative incidence of hospital admissions due to illness (minus accidents).

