Other Outcomes Measures: Hospitalisation for COVID-19; hospitalisation for respiratory infections; COVID-19 infection episodes; Furthermore, we will study the effect on Death for any reason, Death due to documented COVID infection. Cumulative incidence of infectious disease episodes, in particular respiratory infections. Cumulative incidence of infectious hospital admissions, in particular respiratory infections. Cumulative incidence of hospital admission due to documented COVID-19. Cumulative incidence of all-cause and infectious intensive care admission. Cumulative incidence of intensive care admission due to documented COVID infection.

Baseline data collection

Enrolment data regarding chronic illnesses and treatment, lifestyle (family structure, socioeconomic factors, smoking), vaccination history including previous BCG vaccination. Blood sample for SARS-CoV-2 serology.

Follow-up

Follow-up will last for 6 months (182 days). Telephone interviews every second week, regarding symptoms, absenteeism and causes, COVID-19 testing (if done) and their results. Supplemented by daily workplace presence registry information (where present).

End of follow-up

At the end of follow-up, participants will be invited back to the room of the healthcare facility where they were recruited to have another SARS-COV-2 antibody test and to complete the final questionnaire; also, at this time, the research officer will be asked to inspect and report how scarification is in the deltoid area of the right upper limb of the HCW, which may occur due to the BCG vaccine. Information regarding the treatment (BCG or placebo) will be disclosed to the participant at this time.

Sample size

The sample size was calculated on the basis of the primary hypothesis. A total of 1050 HCW randomized with an estimated loss to follow-up of 5%, and a mean number of days off work due to illness in the control group of 5 days (SD=5) over a 6-month period will demonstrate a reduction among BCG vaccinated of 20% for a mean absence of 4 days (80% power and alpha 0.05). The estimated loss to follow-up (5%) was based on past telephone-based surveys conducted in Bissau.

Statistical analysis.

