Data will be reported quantitatively. All analyses will be performed from the intention-to-treat principle. Missing data on background variables will be dealt with by multiple imputation. Final data analysis will begin when the last participant in the multicentric RCT has completed the follow-up period. The primary endpoint, work absenteeism due to illness, will be reported as the total number of sick days with standard deviation. Continuous baseline characteristics will be reported as means with the standard deviation or medians with the inter-quartile range, as appropriate. Categorical baseline characteristics will be reported as count and percentage. Statistical testing for baseline characteristics will be performed. Days of absenteeism will be analysed using a Bayesian negative binomial regression with a fixed effect for BCG, hospital, professional category, age, enrolment week and number of average workdays per week. Incidence data will be analysed in Cox proportional hazards models. Monthly, data on absenteeism by randomization group will be reported to the DSMB.

Trial registration

The trial is registered at clinicaltrials.gov. (<https://clinicaltrials.gov/ct2/show/NCT04641858>)

Funding

EDCTP is funding the run-in costs for the BCG-COVID-RCT, including trials in the respective countries and for training and management.

Study management, monitoring and quality control

The project is led by an International Steering Committee (ISC) consisting of PIs in each of the five countries involved: [name] (international coordinator), PI from Denmark; [name], PI from Guinea-Bissau; [name], PI from Portugal; [name], PI from Cape Verde; and [name], PI from Mozambique. The overall coordination is the responsibility of the Danish partner. The leader has extensive leadership experience from running a Center of Excellence in Denmark and the research group of the Bandim Health Project in Bissau for many years. The Bandim Health Project has a history of past collaboration with the Portuguese partner. The research group will hold teleconferences at least once a week with a formal pre-established agenda on training, enrollment, follow-up, losses to follow-up, staff turnover, vaccine logistics, quality control of data collection, data entry and database management, interim analysis, communication and dissemination activities, other risks. Decisions from each meeting are recorded by the coordinator.

2. Definitions

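### The primary model leaves out recent absence before enrolment, which SAP Table 2 already lists as collected; adding it would be a low-cost and probably modest gain in precision.

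*SAP*

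**What the plan says.** The primary outcome is "Total numbers of days of unplanned absenteeism from work due to illness" (SAP, Outcomes). Three places state the primary model in full:

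- Protocol, Statistical methods, Data analysis: "Total days of absenteeism will be analysed using a Bayesian negative binomial regression with a fixed effect for BCG, hospital, professional category, age, enrolment week", followed by workdays per week.
- SAP opening summary, Statistical analysis: "Days of absenteeism will be analysed using a Bayesian negative binomial regression with a fixed effect for BCG, hospital, professional category, age, enrolment week", followed by workdays per week.
- SAP section 6.4: "a fixed effect for BCG, hospital, professional category, age, enrolment week and number of average workdays per week".

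The lists agree, and none has a term for absence before enrolment. The protocol abstract has a slightly different list, also without one.

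SAP section 7, Table 2 has two relevant baseline rows: "Absent from work for the past 2 weeks due to illness" (no/yes) and "Days absent from work for the past 2 weeks" (quantitative). Their only stated use is summary by arm with a between-arm test.

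SAP section 6.1 allows covariates to be screened at the 20% level, but in the paragraph on logrank and Cox analyses. It does not bring baseline absence into the negative binomial model.

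**The concern.** Workers differ in how often they are off sick. As far as those differences persist, recent absence predicts later absence, and leaving it out of the model leaves that variation in the residual. The interval for the primary ratio is then wider than the collected data require.

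With a log link, adjusting for a pre-randomisation covariate leaves the ratio of means with the same interpretation, provided the effect does not vary with that covariate. The gain therefore costs nothing in interpretation.

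There is also a pre-specification reason. The SAP plans to test baseline absence between arms. A chance imbalance would invite an adjusted analysis chosen after the fact, and fixing the covariates now removes that choice.

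**Working it through.** **Inputs.** Control group: "a mean number of days off work due to illness in the control group of 5 days (SD=5) over a 6-month period". Target: "reduction among BCG vaccinated of 20% for a mean absence of 4 days (80% power and alpha 0.05". 1,050 randomised 1:1 with 5% loss (SAP, Sample size and Randomization), so 1,050 × 0.95 / 2 = 498.75 per arm. Tests are two-sided at 5% (SAP 6.1). Follow-up is 182 days and the baseline window is 14 days.

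**The plan's own sample size.** n per arm = 2 × 5² × (1.960 + 0.842)² / 1² ≈ 393, so 786 in total, and 786 / 0.95 ≈ 828. The stated 1,050 is not reproduced at 80% power. With 1,050 and 5% loss, power on these inputs is 88.5%. (SAP section 3 gives another basis for 1,050, namely 3 × 350; that is a separate matter.)

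**Precision without the baseline term.** Mean 5 and SD 5 imply dispersion k = (25 − 5)/25 = 0.8. The variance of the log ratio is about (1/5 + 1/4 + 2 × 0.8)/498.75 = 2.05/498.75, so the SE is 0.064.

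**What the baseline count can carry.** Its expected mean is m = 5 × 14/182 = 0.385 days. If all excess variance is permanent between-worker difference and sick days fall independently, the proportion of zeros is (1 + 0.8 × 0.385)^(−1/0.8) ≈ 72%. The correlation with the 6-month total is r = (0.8 × 5 × 0.385)/√[25 × (0.385 + 0.8 × 0.385²)] = 0.434. This is close to a ceiling for these inputs.

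**Absence in spells.** If spell lengths are geometric with mean L, the within-worker variance of the total is 5 × (2L − 1). The stable dispersion left over is [25 − 5(2L − 1)]/25. Negative binomial fits to 400 simulated trials per row (998 workers, ratio 0.80, with and without any/none plus log(1 + days)) gave:

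| Mean spell | Stable dispersion | r | SE without | SE with | Change in variance |
|---|---|---|---|---|---|
| 1 day | 0.8 | 0.434 | 0.0639 | 0.0593 | −14% |
| 2 days | 0.4 | 0.14 | 0.0696 | 0.0690 | −2% |
| 3 days | 0 | 0 | 0.0724 | 0.0725 | 0% |

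The estimated ratio stayed at about 0.80 in every row. The share of trials with |z| > 1.96 moved from 94.75% to 95.5%, 89.5% to 90.0% and 89.75% to 90.0%.

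**Varying the stable share instead.** With independent sick days and 100%, 50% or 25% of between-worker variance stable over time, the mean SE went from 0.0641 to 0.0595, 0.0613 to 0.0599 and 0.0614 to 0.0611. Squaring the ratios gives variance reductions of about 14%, 4.5% and 1%.

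**Cross-check on the difference-in-means scale.** With residual SD = 5√(1 − r²), power rises from 88.5% to 88.8% (r = 0.1), 89.7% (r = 0.2), 91.2% (r = 0.3) or 93.9% (r = 0.434). Every r here is an assumption.

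**Limits.** The fits are frequentist and contain none of the other planned covariates, which may already absorb some stable variation. They also ignore the exclusion of workers with fever or suspected infection, which thins out absence just before enrolment. Both make the upper figures optimistic.

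**The case against.** The case against treating this as a defect is strong, and most of it stands. The plan already pre-specifies an adjusted model and states its covariates identically in three places. Nothing is biased. On its own inputs the trial has 88.5% power against a stated 80%, so no shortfall in precision is shown at the 5% level. That margin does not extend to the protocol's 0.995 interim threshold: at one-sided 0.005 and a single look, the same two-means formula needs about 1,230. But that is a reason to welcome precision, not evidence that this covariate supplies much of it.

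Three stronger readings are tempting and are not supported:

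- **A saving of about 160 participants.** This follows from a 7% lower SE: (0.0641/0.0595)² = 1.16, and 0.16 × 998 ≈ 160. It needs all excess variance to be stable and sick days to be independent. The documents do not say that stable differences dominate the overdispersion.
- **That Table 2 holds a baseline value of the outcome itself.** The days row does not say that the absence was for illness. It follows an illness yes/no row, but SAP Table 3 lists the same unlabelled row and, separately, one for days absent through illness. The match is likely, not certain.
- **That chronic disease and the health scale add a further known gain.** Neither has been quantified, and Table 2 treats the health scale as categorical, so a linear term would need its own justification.

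The objection does not remove the core point: a pre-randomisation measure close to the outcome is collected and left out of the primary model.

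**Conclusion.** The point holds as an efficiency suggestion. The primary model omits recent absence, the item is listed as collected, and including it would not be expected to cost precision or alter the meaning of the ratio. The likely gain is modest: about 0% to 14% of the variance of the log ratio, and about 2% or less if spells average 2 days or more. The range assumes the plan's mean and SD and a ratio of 0.80. Where the trial falls within it depends on the stable share and the spell length, neither of which the documents give. Confidence is high on the omission and low on the size of the gain. A reader should not infer that the planned analysis is biased or underpowered because of it.

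**What to change.** Before unblinding, add one sentence to the model in the Protocol (Data analysis), the SAP summary (Statistical analysis) and SAP 6.4, for example: *The model also includes illness absence in the two weeks before enrolment (any or none) and log(1 + days absent in those two weeks).*

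First confirm from the questionnaire that the days item refers to illness; if it does not, use the yes/no item alone. Use the same covariates in the final fit and in any interim fit, because the protocol's stopping rule rests on this model. Check that both items are nearly complete, since SAP 6.2 treats variables with more than 10% missing as unsuitable for imputation. Chronic disease and the health scale may be added as options, with their form fixed in advance.

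The cost is wording in three places and a check of one questionnaire item. No new data or participants are needed.
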